10.3.5.3. Patient Global Assessment of Disease

Two questions will be included for subjects to rate their disease and their disease severity.

Subjects will rate their overall well-being based on a 5-point Likert scale from poor to excellent. Subjects will be asked, “Considering all the ways in which your eczema affects you, indicate how well you are doing.” Response choices are: ‘Poor’, ‘Fair’, ‘Good’, ‘Very Good,’ or ‘Excellent’.

Subjects will also be asked to best describe the overall appearance of skin lesions at a given time point using the vIGA scale (Section 10.3.3). The vIGA scale has been adapted for patients to complete. The scale has been modified for easier understanding for subjects, to exclude medical terminology (eg, lichenification has been adapted to thickening and erythema to redness).

Subjects will complete these assessments at time points according to the [REDACTED].

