The two proportion-based key secondary endpoints (EASI-75 at Week 12 and vIGA response status at Week 12) will be analyzed in the FAS using the Cochran-Mantel-Haenszel method (CMH) adjusted for randomization stratification factors of baseline vIGA score (3 versus 4) and region [REDACTED]. Missing data will be imputed in the FAS using the NRI method: missing dichotomous response status at Week 12 (including those after use of rescue medication) will be imputed using the non-responder imputation (NRI) method, ie, “non-responders” or “failure” for missing response. The number, percentage of subjects achieving the goal and Clopper-Pearson exact 95% confidence intervals will be reported. The differences in proportion between treatment groups, along with p-values and the 95% CIs will also be reported.

The following sensitivity analyses will be performed:

- FAS, MI

Missing Week 12 EASI-75 response status will be derived based on the multiple imputed datasets for EASI values as described above. The same CMH test will then be performed for EASI-75 and combined using Rubin’s method. Combined proportion along with the 95% CI, and p-value will be reported.

- mFAS, using OC (observed data regardless of rescue medication uses and without imputation)

Response endpoint at Week 12 will be analyzed using a logistic regression model including treatment group as factor, Baseline EASI score and the two randomization factors of baseline vIGA (3 versus 4) and region [REDACTED] as covariates. Odds ratio of etrasimod versus placebo along with the p-value and 95% CI will be reported.

The same CMH test as described above will be performed for the key secondary endpoints, using the following:

- PPS, using OC
- TCS, using OC

D. Other Secondary Efficacy Outcome Analyses

Secondary efficacy endpoints will be analyzed using the below methods:

[figure not shown]

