- Longitudinal continuous variables (percent change in weekly peak pruritus NRS, change and percentage change in %BSA) measured at visits (weeks) up to Week 12 will be analyzed with a MMRM model based on FAS using observed data. The MMRM model will include treatment group, visit (week), and interaction of treatment-by-visit (week) as factors, and baseline measure and randomization stratification factors as covariates. An unstructured covariance matrix will be specified for the MMRM model. If the model does not converge using an unstructured covariance matrix, an auto-regressive AR(1) structure will be tested. If AR(1) fails to converge, a compound symmetric structure will be used. LS means at visit (week) and LS mean differences at visit (week) between treatment group with p-values and corresponding 95% CIs will be reported.
- Dichotomous measures (weekly peak NRS ≥ 3 reduction, EASI-50, and EASI-90) at Week 12 will be analyzed in the same way as for the key secondary endpoints based on FAS with CMH method adjusted for randomization stratification factors of baseline vIGA score (3 versus 4) and region [REDACTED]. Missing data (including those after use of rescue medication) will be handled by NRI method. The number, percentage of subjects achieving the goal and Clopper-Pearson exact 95% confidence intervals will be reported. The differences in proportion between treatment groups, along with p-values and the 95% CIs will also be reported. Weekly peak NRS ≥ 3 reduction will be assessed among the subset of subjects whose baseline peak NRS is ≥ 3 .

Sensitivity analyses will be performed in the PPS and TCS using observed data.

E. Exploratory Efficacy Outcome Analysis

Below exploratory endpoints will be analyzed in a similar manner as the secondary continuous variables with the MMRM model based on FAS using observed data.

- Change in DLQI from Baseline to Week 12.
- Change in POEM from Baseline to Week 12.
- Percent change in SCORAD total and individual symptom scores from Baseline to Week 12.

The primary and sensitivity analysis for all efficacy endpoints are summarized in **Table 3**.

Table 3 Summary of Efficacy Analyses

Efficacy Endpoint	Primary Analysis	Sensitivity Analysis
DB Treatment Period		
Primary		

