A post hoc analyses set (PHAS) will be defined by excluding 9 subjects [REDACTED] from the full analysis set in the 2mg etrasimod group. The efficacy of treatment in these subjects were impacted by unwarranted dose interruption between week 4 and 8. The following analysis will be repeated using the post hoc analysis set:

- The primary outcome (percentage change in EASI from Baseline to Week 12) will be analyzed using the same ANCOVA and MMRM model described in [section 8 \(subsection B\)](#).
- EASI-75 and VIGA response rate (i.e. proportion of subjects achieving a validated Investigator's Global Assessment (vIGA) of 0 or 1 (on a 5-point scale) and a reduction from Baseline of ≥ 2 points) will be analyzed using the same CMH analysis described in [section 8 \(subsection C\)](#).
- Percentage in weekly peak NRS will be analyzed with the same MMRM model described in [section 8 \(subsection D\)](#).
- Weekly peak pruritus NRS with ≥ 3 and ≥ 4 reduction will also be analyzed with the same CMH analysis described in [section 8 \(subsection C\)](#).

B. Additional Exploratory Outcomes

The following additional outcomes will be explored:

- Proportion of subjects achieving an improvement (reduction) of ≥ 4 points in POEM from Baseline to Week 12.
- Proportion of subjects achieving an improvement (reduction) of ≥ 4 points in DLQI from Baseline to Week 12.
- Proportion of subjects achieving an improvement (increase) of ≥ 2 points in PGA from Baseline to Week 12.
- Proportion of subjects achieving an improvement (reduction) of ≥ 3 points in office based peak pruritus from Baseline through Week 12
- Proportion of subjects achieving an improvement (reduction) of ≥ 4 points in office based peak pruritus from Baseline through Week 12

The above outcomes will be analyzed in the FAS and the PHAS using the Cochran-Mantel-Haenszel method (CMH) adjusted for randomization stratification factors of baseline vIGA score (3 versus 4) and region [REDACTED]. Missing data will be imputed using the NRI method. The number, percentage of subjects achieving each outcome and Clopper-Pearson exact 95% confidence intervals will be reported. The differences in proportion between treatment groups, along with p-values and the 95% CIs will also be reported.

[figure not shown]

C. Sensitivity Analysis for Percent Change in EASI

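### SAP 12.A refers the weekly itch responders to 8.C, without the baseline minimum set in 8.D, and the 12.B itch, POEM and DLQI responders state none, so subjects who cannot respond count as failures

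*SAP*

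**What the plan says.** **Weekly diary itch, main analysis.** SAP 8.D analyses the ≥3-point responder by the 8.C method (CMH, non-responder imputation) and adds a restriction: "Weekly peak NRS ≥ 3 reduction will be assessed among the subset of subjects whose baseline peak NRS is ≥ 3". This is the only baseline minimum in 8.D.

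**Weekly diary itch, post hoc set.** SAP 12.A opens with "The following analysis will be repeated using the post hoc analysis set" and then states: "Weekly peak pruritus NRS with ≥ 3 and ≥ 4 reduction will also be analyzed with the same CMH analysis described in". The cross-reference given there is to 8.C. The bullet just before it refers the continuous weekly itch endpoint to 8.D instead.

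**The section referred to.** SAP 8.C covers EASI-75 and vIGA response, which "will be analyzed in the FAS using the Cochran-Mantel-Haenszel method (CMH) adjusted for randomization stratification factors". It has no baseline subset, and those two endpoints need none.

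**Other post hoc responders.** SAP 12.B adds responders of ≥3 and ≥4 points on office-based peak itch, ≥4 points on DLQI, and the following on POEM: "Proportion of subjects achieving an improvement (reduction) of ≥ 4 points in POEM from Baseline to Week 12". All are analysed in the whole FAS and the whole PHAS with non-responder imputation, and no baseline minimum is stated.

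**Entry criteria.** Protocol 4.1 sets minima for EASI, vIGA and BSA. The inclusion criteria set none for itch, POEM or DLQI.

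**PGA.** SAP 12.B lists "Proportion of subjects achieving an improvement (increase) of ≥ 2 points in PGA from Baseline to Week 12" without naming the item. SAP 8.A says the PGA has two questions, wellness and appearance, and lists response choices for wellness only (Poor to Excellent), with no numeric codes. For appearance, Protocol 10.3.5.3 says: "Subjects will also be asked to best describe the overall appearance of skin lesions at a given time point using the vIGA scale".

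**The concern.** A subject whose baseline score is below k cannot fall by k points. Kept in the denominator, that subject is a certain failure in whichever arm he or she was randomized to. The 8.D restriction deals with this for the ≥3-point diary itch endpoint. The reference in 12.A leads to a section without the restriction, and 12.B does not mention one.

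Two things are at stake. For weekly itch ≥3, the purpose of the PHAS is to show what happens when nine subjects are removed from the 2 mg arm. If the denominator rule changes at the same time, the FAS and PHAS results differ for two reasons that cannot be separated. For all the post hoc itch, POEM and DLQI responders, the reported rates and risk differences are lower than they are among subjects who could respond.

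**Working it through.** The plan gives no figure for these analyses, so there is none to reproduce for them. Its only design figure is for the primary endpoint: difference 35, SD 41, one-sided 0.025. A two-sample t-test then needs 30 evaluable subjects per arm (power 0.902), and 30/(1−0.25) = 40 per arm. That agrees with the SAP and is not affected by this point. The 40 per arm is used below.

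**Step 1: which denominator applies where, read literally**

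| Endpoint | FAS | PHAS |
|---|---|---|
| Weekly itch ≥3 | baseline ≥3 (8.D) | whole set (12.A, via 8.C) |
| Weekly itch ≥4 | no analysis visible | whole set (12.A, via 8.C) |
| Office itch ≥3, ≥4 | whole set (12.B) | whole set (12.B) |
| POEM ≥4, DLQI ≥4 | whole set (12.B) | whole set (12.B) |

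Only the first row changes its rule between sets.

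**Step 2: size of the dilution**

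Let f be the share below the threshold and p the responder rate among subjects able to respond. The whole-set rate is (1−f)p. With f equal in both arms:

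- risk difference = (1−f)(p_active − p_placebo)
- risk ratio = (1−f)p_active / [(1−f)p_placebo] = p_active / p_placebo

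The documents give neither f nor p. Assume 45% against 25% among subjects able to respond:

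- f = 5%: 42.75% − 23.75% = 19 points
- f = 10%: 40.5% − 22.5% = 18 points
- f = 20%: 36% − 20% = 16 points

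The risk ratio is 1.8 throughout.

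**Step 3: the FAS and PHAS contrast for weekly itch ≥3**

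On the same assumptions with f = 10%, the FAS analysis with the minimum shows 20 points and a PHAS analysis without it shows 18. That 2-point gap comes from the denominator alone, before any effect of removing nine subjects.

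**Step 4: effect on power**

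Assume 50% against 25% among subjects able to respond, 40 per arm and a two-sided 0.05 test. With f = 0 the power is 0.641.

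| f | Difference without minimum | Power without minimum | Power with minimum |
|---|---|---|---|
| 5% | 23.75 points | 0.605 | 0.618 |
| 10% | 22.5 points | 0.569 | 0.594 |
| 20% | 20.0 points | 0.497 | 0.544 |

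The analysis with the minimum is ahead by about 1 to 5 percentage points, even though it uses fewer subjects.

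**Step 5: unequal f**

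Randomization makes f equal only in expectation, and the PHAS removes subjects from one arm. With 50% against 25%:

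- f of 0% active and 10% placebo: 50 − 22.5 = 27.5 points
- f of 10% active and 0% placebo: 45 − 25 = 20 points

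Against a true 25 points, the error can go either way.

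**Step 6: PGA**

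If wellness is coded 1 to 5 from Poor to Excellent, a rise is improvement, and a rise of 2 is impossible from Very Good or Excellent. The vIGA scale behind the appearance item runs from 0 (clear) to 4 (severe), so improvement there is a fall. A rule stated as an increase therefore fits one item only, and the SAP does not say which.

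**The case against.** The strongest reply is that nothing was removed. 12.A says the analyses are repeated, and 8.D itself uses the 8.C method and adds the subset as a rule for this one endpoint. Citing 8.C for the CMH analysis is thus compatible with keeping the subset. SAP Table 3 lists the ≥3 endpoint under FAS with CMH without mentioning the subset, so a bare method reference proves little. This stands in part: for weekly itch ≥3 the text is ambiguous, not an explicit deletion. It does not settle the ≥4 version, because 8.D has no ≥4 analysis to repeat.

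A second reply is that Protocol 11.4.1 includes all FAS subjects in dichotomous analyses, so the whole-set denominator is the general rule and the 8.D subset is the exception. That is fair. Both are valid randomized comparisons, which is a reason to show both. It does not justify using the exception for diary itch and not for the same threshold on office itch.

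A third is that f may be small. A POEM score below 4 means clear, almost clear or the lowest mild score, which should be uncommon in subjects entering with EASI ≥16, vIGA ≥3 and BSA ≥10%. For POEM the lower end of the assumed range, or less, is more plausible.

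Some stronger readings are tempting, but the documents do not support them:

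- **That Section 12 dropped a minimum for itch ≥4, POEM, DLQI or office itch.** None was ever specified. POEM and DLQI are continuous MMRM endpoints in 8.E.
- **That the FAS and PHAS contrast is confounded throughout.** The 12.B outcomes use one rule in both sets. No FAS analysis of diary itch ≥4 is visible, and some exploratory endpoints are redacted.
- **That the PGA rule counts worsening as response.** The bullet speaks of improvement, and wellness is the only item whose choices the SAP lists. The fault is an unnamed item, which is a different matter from dilution.

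**Conclusion.** The point holds as a minor one. 8.D has a baseline minimum for weekly itch ≥3. The 12.A reference leads to a section without it, and the ≥4 version and the 12.B itch, POEM and DLQI responders have no stated minimum. With equal f across arms, each risk difference shrinks by (1−f). On assumed rates of 45% against 25% and f of 5% to 20%, 20 points become 19 to 16. Both the rates and f are assumptions.

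A reader might infer that the missing minimum flatters etrasimod. It does not: with equal f the difference moves toward zero and the risk ratio stays the same. With unequal f the direction is unknown. The analyses are post hoc, exploratory and unadjusted for multiplicity. The primary and key secondary results do not depend on them.

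**What to change.** - **SAP 12.A:** refer the weekly itch responder analyses to 8.D, with baseline peak NRS ≥3 for the ≥3 endpoint and ≥4 for the ≥4 endpoint.
- **SAP 12.B:** apply the matching baseline minimum to office-based itch (≥3 and ≥4) and to POEM and DLQI (≥4), in both the FAS and the PHAS.
- **Reporting:** show the whole-set result beside each restricted one and label the change as post hoc, so that a denominator chosen at this stage does not stand alone.
- **PGA, wording only:** state that the ≥2-point increase applies to the wellness item and give its numeric coding. No new appearance responder is needed.

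The cost is SAP wording and a subset flag from baseline scores already collected, with slightly smaller denominators in the restricted analyses. SAP section 1 allows amendment for ad hoc analyses before the final database lock.

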It is assumed that the percent change in EASI from Baseline to Week 12 will be normally distributed with an estimated standard deviation (SD) of 41%. Assuming a 1:1:1 randomization, 120 subjects (40 subjects each in 1 mg etrasimod, 2 mg etrasimod, and placebo groups) is sufficient to achieve at least 90% power to detect a difference of 35% in EASI from Baseline to Week 12 between each of the etrasimod treatment groups and placebo by a 2-sample t-test using a 1-sided significance level of 0.025. This sample size also accounts for an estimated drop-out rate up to 25%.

D. Treatment Randomization

Randomization will be stratified by vIGA score at Baseline (3 versus 4) and region

E. Assessment Schedule

For the statistical analysis, DB Treatment Period will include 12 weeks treatment and 4 weeks safety follow-up; OLE Period will include 52 weeks treatment and 4 weeks safety follow-up. The date at which the subject is randomized will be referred to as the “Baseline/Day 1”. Subjects will be requested to attend the following scheduled visits for the DB Treatment Period from their Baseline/Day 1 visit: Week 1, 2, 4, 6, 8, 12 and Week 16/SFU visit. For the OLE Period, Week 16 (this will be same as Week 16 in the DB Treatment Period), Week 17, 18, 20, 24, 28, 32, 40, 48, 56, 68, and Week 72/ SFU. The acceptable visit window for scheduled visits for the DB Treatment Period including Week 16, and Week 17 and 18 in OLE Period is ± 3 days, for all the other OLE visits, the scheduled visit window is ± 7 days. Visits that subjects make to the clinic outside the visit window are recorded as unscheduled visits.

Please refer to protocol for details.

5. General Analytical Considerations

A. Data Sources and General Rules

Data are recorded on electronic case report form (eCRF) for each subject screened/enrolled in this study. These forms will be used to transmit information collected during the study to the Sponsor and regulatory authorities, as applicable. Laboratory data, [REDACTED] blood samples and [REDACTED] data are collected separately by the selected vendors. Section 14 of the protocol provides additional details regarding data handling and record keeping.

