Statistical analysis will be performed following IQVIA Biotech standard operating procedures and on the IQVIA Biotech computer network. All statistical analysis will be performed using SAS Version 9.4 with program code prepared specifically for the project by qualified IQVIA Biotech statisticians and SAS programmers.

All observed and derived variables (e.g., change from baseline, percentage change from baseline, and response status) that are analyzed or summarized will be listed by subject. Descriptive statistics will provide an overview of the efficacy and safety results. For categorical parameters, the number and percentage of subjects in each category will be presented. For continuous parameters, descriptive statistics will include number of subjects, mean, SD median, minimum, and maximum.

B. Definition of Baseline and Study Day

Study day will be defined separately for the DB Treatment Period and OLE Period. For all subjects, Day 1 is the date of first study drug administration in the DB Treatment Period. This will be referred to as the **Overall Day 1**. For those enrolling into the OLE Period, an **OLE Day 1** will be additionally defined as the date of the first study drug administration in the OLE Period at Week 16.

Study day will be calculated relative to the date of Overall Day 1.

Similarly, Baseline will be defined separately for DB Treatment Period and OLE Period as follows:

[figure not shown]
- **DB Treatment Period:** baseline will be defined as the last available measurement prior to the first dose of the study drug in DB Treatment Period. Specifically, for vital signs (resting heart rate (HR), blood pressure (BP), body temperature, and respiratory rate) and [REDACTED], the Day 1 pre-randomization assessments will be used as baseline measurements. The lowest pre-dose HR measurement will be used for comparison to the post-dose HR measurement. This will be referred to as the **DB baseline**.

[figure not shown]
- OLE Period: for those enrolling into the OLE Period, an **OLE baseline** will be additionally defined as the last pre-dose measurement at Week 16 at Week 16.

Change from baseline is defined for both DB Treatment Period and OLE Period as the post-baseline value minus the baseline value unless otherwise specified. Percent change from baseline is calculated as follows: Percent change = (Change from baseline / Baseline) x 100.

C. Analysis Visit Window

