Additional sensitivity analysis for percent change in EASI will be performed with observed cases in the FAS using the MMRM model described in [section 8 \(subsection B\)](#)

D. Additional Subgroup Analyses for EASI-75 and vIGA

Prior Systemic Failure Subject (Yes, No)

Prior Systemic Failure Subject are subjects who previously had ineffective/intolerant therapy in oral steroid, oral JAK and Dupilumab, or other conventional Systemic therapy:

- 15 subjects in the 2mg etrasimod group: 

- 3 subjects in the 1mg etrasimod group: 

- 10 subjects in the placebo group: 

EASI-75 and vIGA response rate by visit will be analyzed for the subgroups of Prior Systemic Failure Subject (Yes, No) and using the same CMH analysis described in [section 8 \(subsection C\)](#).

13. References

Carpenter, J. R. and Kenward, M. G. (2013), *Multiple Imputation and Its Application*, New York: John Wiley & Sons.

Ruberg SJ. Dose Response Studies. II. Analysis and Interpretation. *J Biopharm Stat* 5(1), 15-42 (1995).

van Buuren S. Multiple imputation of discrete and continuous data by fully conditional specification. *Stat Methods Med Res.* 2007;16(3):219-242.

Appendix 1

B. Summary of Plasma Concentrations

Concentrations below the limit of quantification (BLQ) will be assigned a numerical value of zero for the calculation of descriptive statistics and plotting of concentrations. For geometric mean and geometric %CV, the zero values will be excluded.

Individual subject etrasimod plasma concentrations will be presented in the data listings (showing treatment received, sex, age, scheduled nominal time, and actual time) and also summarized using descriptive statistics (n, mean, SD, % Coefficient of Variance [CV], geometric mean, geometric %CV, minimum, median, and maximum) for each scheduled visit, as following:

- For timepoints in the DB Treatment Period (Baseline/Day 1 to Week 16), by actual treatment received in DB Treatment Period
- For timepoints in OLE Period (Week 16 to Week 72), by actual treatment received in DB Treatment Period and overall

Mean (SD) plasma concentrations will be plotted versus scheduled nominal time from start of treatment on both linear and semilogarithmic scales according to the above summaries.

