Individual subject plasma concentrations will be plotted (in both linear and semilogarithmic scales) versus actual time from start of treatment, for timepoints in DB Treatment Period (Baseline/Day 1 to Week 16) and for timelines in OLE Period (Week 16 to 72), separately.

C. Steady-State (SS) Concentration Analysis

Steady-state (SS) concentration will be assessed for the DB Treatment Period and OLE Period separately. Individual subject SS pre-dose (trough) plasma concentrations will be averaged across ($C_{ss,avg\ trough}$) across the timeframe shown by the statistical model to be steady state; for the DB portion, out to a maximum timeframe of 12 weeks, and in the OLE out to a maximum of 68 weeks. Only C_{trough} values in the range of steady state will be averaged into $C_{ss,avg, trough}$. Individual SS pre-dose concentrations will be included in the data listings and summarized using descriptive statistics as described above for DB Treatment Period and for OLE Period separately (except with respect to scheduled nominal time which is not applicable).

Box plots of SS pre-dose (trough) plasma concentrations will be plotted versus scheduled nominal time for each scheduled nominal visit, by treatment received in DB Treatment Period and overall.

Box plot of $C_{ss,avg\ trough}$ will be plotted by treatment received in DB Treatment Period and overall.

Scatter plot matrices, stratified by treatment, of individual subject $C_{ss,avg\ trough}$ values versus baseline body weight and age will also be plotted, and showing correlation coefficient (Spearman's rank correlation coefficient) and p-value.

Etrasimod plasma steady-state will be determined by regressing trough (pre-dose) concentration values over time for the DB Treatment Period (Baseline/Day 1 to Week 16) and OLE Period (Week 16 to Week 72) separately and the resultant slope will be tested for its difference from zero. For each treatment period, a set of data ranged by weeks will be fitted using a mixed effect model with Treatment group (for DB Treatment Period) and week (as a continuous covariate) as fixed effect terms and subject as a random effect term. Steady state is estimated to be achieved as the earliest week included in the analysis when the 90% CI of the slope includes 0.

D. Exposure-Response Relationship Analysis

To explore potential etrasimod plasma exposure-response relationships, the following will be generated, and Baseline below refers to DB Baseline:

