- Scatter plot matrix of individual subject change from baseline in EASI Score at Week 12 values versus corresponding individual subject pre-dose (trough) concentrations at Week 12, and showing correlation coefficient r - and p-value (Spearman's rank correlation coefficient). The same approach will also be used to generate another set of similar scatter plots but using instead

individual subject $C_{ss,avg}$ trough concentrations (rather than Week 12 predose concentrations).

█ [REDACTED]

█ [REDACTED]

- Overlay plot showing profiles of mean (SD) heart rate absolute change from baseline (first dose cardiac monitoring) and mean (SD) plasma concentration versus scheduled nominal time from start of treatment for Day 1 will be plotted by DB treatment. A similar set of overlay plots will also be generated instead using mean (SD) heart rate (beats/min) and mean (SD) heart rate percent change from baseline values (ECG data).
- Overlay plot showing profiles of mean (SD) heart rate absolute change from baseline (first dose cardiac monitoring) and mean (SD) plasma concentration versus scheduled nominal time from start of treatment for Week 16 will be plotted by DB treatment. A similar set of overlay plots will also be generated instead using mean (SD) heart rate (beats/min) and mean (SD) heart rate percent change from baseline values (ECG data).
- A scatterplot of individual heart rate versus individual etrasimod plasma concentration from start of treatment for Day 1 and all scheduled nominal time by DB treatment, depicting regression relationship, will be generated; treatment groups will be denoted using different symbols but a single regression presented.

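### The double-blind steady-state PK regression is written as running to Week 16, four weeks off drug, while averaging in the same section stops at Week 12

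*SAP*

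**What the plan says.** SAP Appendix 1.C fits a mixed model, with subject as a random effect and week as a continuous covariate, by "regressing trough (pre-dose) concentration values over time for the DB Treatment Period (Baseline/Day 1 to Week 16". The decision rule is: "Steady state is estimated to be achieved as the earliest week included in the analysis when the 90% CI of the slope includes 0". Troughs inside the resulting range are then averaged per subject, "for the DB portion, out to a maximum timeframe of 12 weeks, and in the OLE out to a maximum of 68 weeks".

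On timing, SAP 4.E states that the "DB Treatment Period will include 12 weeks treatment and 4 weeks safety follow-up". Protocol 9.2.4 places the Week 16 visit 4 weeks after the last dose. The OLE schedule in SAP 4.E opens with "Week 16 (this will be same as Week 16 in the DB Treatment Period", and SAP 5.B adds an OLE Day 1 that "will be additionally defined as the date of the first study drug administration in the OLE Period at Week 16". Concentrations are expected at that visit: Appendix 1.D plans an overlay in which "mean (SD) plasma concentration versus scheduled nominal time from start of treatment for Week 16 will be plotted by DB treatment".

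On values below the limit of quantification (BLQ), Appendix 1.B says that they "will be assigned a numerical value of zero for the calculation of descriptive statistics and plotting of concentrations". The visible text does not extend that rule to the mixed model.

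**The concern.** One section carries two end points: Week 16 for the regression that decides which weeks are at steady state, and Week 12 for the averaging that follows. A Week 16 sample says nothing about steady state on treatment. If it is in the fit with a value at or near zero, it pulls the slope down from every on-treatment start week. Dropping early weeks makes the pull stronger, so the search cannot correct itself.

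At stake is the average steady-state trough. If no steady-state range is found, it has no input. If the range is declared to start at Day 1, a pre-first-dose zero can enter each subject's average. That average feeds its own listing and box plot, the weight and age correlations with p-values, and one of the two EASI exposure-response plots in Appendix 1.D.

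**Working it through.** **Inputs.** Half-life about 33 h with washout within a week (Protocol 10.5.7.3). Week 16 at 28 days after the last dose (Protocol 9.2.4). Double-blind visits at Day 1 and Weeks 1, 2, 4, 6, 8, 12, 16 (SAP 4.E). The PK sampling schedule is not visible, so treating every visit as a trough time is an assumption.

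**1. The protocol's washout figure.** 7 days = 168 h; 168/33 = 5.09 half-lives; 2^-5.09 = 2.9% remaining. This agrees with washout within a week.

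**2. Week 16.** 28 × 24 = 672 h; 672/33 = 20.4 half-lives; 2^-20.4 ≈ 7 × 10^-7 of the on-treatment value, effectively zero. On the same half-life, troughs reach 97% of steady state by Week 1 and 99.9% by Week 2.

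**3. Noise-free slopes.** Slope = Σ(x − x̄)y / Σ(x − x̄)², with y as a fraction of the steady-state trough and every subject sampled at every visit. Example for Weeks 8, 12, 16 with y = 1, 1, 0: x̄ = 12, so (−4 × 1 + 0 × 1 + 4 × 0)/(16 + 0 + 16) = −4/32 = −12.5% per week.

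| Start week | Ending Week 16, % per week | Ending Week 12, % per week |
|---|---|---|
| Day 1 | −1.63 | +4.41 |
| 1 | −4.95 | +0.16 |
| 2 | −5.88 | +0.01 |
| 4 | −7.33 | 0.00 |
| 6 | −9.32 | 0.00 |
| 8 | −12.5 | 0.00 |
| 12 | −25.0 | not defined |

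The Day 1 row explains the second failure. With no Week 16 samples the Day 1 slope is +4.41, and with all of them it is −1.63. At some share in between the two zeros cancel, and the rule can accept Day 1.

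**4. The rule in simulation.** Assumptions, none from the documents: random-intercept model on the untransformed scale; earliest week dropped until the 90% CI covers 0, end week fixed; four PK schedules; between/within CV of 25%/15% or 60%/40%; 20 or 40 subjects per dose; 25% drop-out before Week 12; Day 1 and off-drug Week 16 values equal to zero. There were 16 scenarios × 200 = 3,200 trials per row.

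| Share of etrasimod subjects with a Week 16 pre-dose sample | On-treatment week selected | Range by scenario |
|---|---|---|
| 5% | 2,487 (77.7%) | 19.5–100% |
| 10% | 1,194 (37.3%) | 0–89% |
| 25% | 128 (4.0%) | 0–19% |
| 40% | 10 (0.3%) | 0–2.5% |
| 50%, 60%, 75% | 0 | 0 |
| Range ended at Week 12, Day 1 zeros kept | 3,137 (98.0%) | 95.5–100% |
| BLQ values left out of the fit | 3,128 (97.8%) | 95.0–100% |

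At a 60% share, 521 trials found no steady state and 2,679 selected Day 1. By scenario each outcome ran from 0% to 100%. With every subject sampled at Week 16 (30 per arm, three noise settings, 200 runs each), 94–100% of runs found no steady state and at most 6% selected Day 1. Which failure occurs is therefore not predictable from the documents. That the rule misses the on-treatment weeks is the stable result once the share is about 25% or more.

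**5. Effect if Day 1 is selected and counted as zero.** The 12-week cap still keeps Week 16 out of the average. One zero among 7 pre-dose samples gives 1/7 = a 14% fall; among 5, 20%; among 4, 25%.

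**The case against.** The strongest reply is that the parenthesis is only a period label. Appendix 1.B uses the same one for the concentration summaries, and the regressed variable is called a trough, which a sample 28 days after the last once-daily dose is not in any ordinary sense. The 12-week limit can also be read as bounding the steady-state timeframe itself, and the model is fitted to data ranged by weeks, so the end week need not be fixed at 16. Finally, the PK schedule and SAP Section 10 are redacted and the visible Appendix 1 begins at part B, so an exclusion may already be written there.

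Much of this stands, and it limits the point to what the visible text permits. It does not remove it. As a period label the parenthesis still takes in Week 16, because SAP 4.E counts the follow-up weeks as part of the period. No visible words tell a programmer to drop the sample. Either failure would probably be noticed in the output, but the range would then have to be chosen after seeing the data.

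A reader might infer three stronger things that the documents do not support:

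- **That the plan has no BLQ rule for the model.** The visible text shows none, but redacted text may hold one.
- **That the regression is bound to fail.** That needs off-drug values entered as zero and enough Week 16 samples; with BLQ values left out, the fit behaves.
- **That the open-label range to Week 72 has the same fault.** No dose follows that visit, so its sample is not pre-dose, and no harm was shown there.

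**Conclusion.** The point holds as a minor inconsistency. The written double-blind regression range reaches a visit 4 weeks off drug, and it disagrees with the averaging limit in the same section. If off-drug values enter as zero for about 25% or more of etrasimod subjects, the rule selects an on-treatment week in at most 4.0% of simulated trials overall. Below that share the result depends heavily on the scenario.

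These figures rest on the assumed schedules, CVs, untransformed scale and fixed end week. The slope calculation rests only on the half-life, the visit weeks and full sampling at every visit. The effect is confined to exploratory PK output. The EASI plot on Week 12 pre-dose concentrations and all efficacy and safety comparisons are untouched.

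**What to change.** Add a sentence to SAP Appendix 1.C stating that the double-blind steady-state regression uses on-treatment troughs from the first post-dose visit to Week 12, in line with the averaging limit already given. If redacted text already says this, a cross-reference is enough. Washout and pre-first-dose values then no longer reach the double-blind fit, so the choice of BLQ rule for the model ceases to decide its result. The open-label range needs no change.

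The cost is one sentence and a data filter. The excluded samples leave this regression only and stay in the listings, summaries and concentration plots.
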